3.1 Inclusion Criteria

3.11 Age ≥ 18 years.

3.12 Histological confirmation of expressing CD20 antigen (Cheson et al.,1999) as determined by pathology at the respective institution and central pathology review at Mayo Clinic Rochester.

NOTES:

- For Phase I, all types of B-cell lymphomas are allowed to participate.
- For phase II, only DLBCL patients are allowed to participate.
- For Phase I *only*, patients with primary mediastinal large B-cell (PMLBCL) or transformed lymphoma are allowed to participate.

ADDITIONAL NOTES REGARDING SLIDE SUBMISSION:

- Central pathology review is mandatory, but is retrospective in nature. Slides must be submitted ≤ 30 days after registration to allow for confirmation of DLBCL diagnosis and to have sufficient material for GCB/ABC assessment by a gene-expression profiling method (see Section 17).
- Patients *can* be enrolled prior to submission of slides.
- For Phase II, if central review of pathology shows that the patient does NOT have DLBCL or the amount of FFPE material is not considered sufficient for COO analysis, the patient may remain on the study but the patient should be replaced.

3.13 Measurable disease (at least 1 lesion ≥ 1.5 cm in diameter) as detected by PET/CT and as defined in Section 11.0.

3.15 Only 1 line of previous anti-lymphoma therapy is allowed and not currently receiving any other agent that would be considered as a treatment for the lymphoma. Patients must be ≥ 2 weeks from prior anti-lymphoma therapy. The use of steroids and/or rituximab up to 1 week prior to registration for management of symptoms is allowed.

3.16 ECOG Performance Status (PS) 0-2. (Form available on the ACCRU web site:

3.17 Adequate organ function as defined by the following laboratory values obtained ≤ 7 days prior to registration.:

- Absolute neutrophil count (ANC) $\geq 1500/\text{mm}^3$
- Platelet count $\geq 75,000/\text{mm}^3$
- Total bilirubin $\leq 2 \times \text{ULN}$ (unless related to lymphoma or Gilbert's disease) OR $\leq 5 \times \text{ULN}$ for subjects with documented or suspected Gilbert's disease, or related to involvement of the liver by the lymphoma.
- Aspartate transaminase (AST) and ALT (SGPT) $\leq 3 \times \text{ULN}$ unless evidence of the direct liver and/or bone involvement by lymphoma, then $\leq 5 \times \text{ULN}$
- Renal function assessed by calculated creatinine clearance as follows (see Appendix: Cockcroft-Gault estimation of CrCl):

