11.0 Treatment Evaluation Using PET/CT Cheson's response criteria for malignant lymphoma

11.1 Response Considerations (Lymphoma)

Schedule of Evaluations: For the purposes of this study, patients should be evaluated for response at cycle 2 day 21.

Definitions for clinical response for patients with lymphoma are from the recently revised Cheson's et al criteria published in 2014, derived from the original criteria published in 2007 (Cheson, 2014 and Cheson, et al 2007). Lymph node measurements should be taken from the CT portion of the PET/CT, or other dedicated CT scans where applicable. Measurement of lymphadenopathy will be determined by adding the sum of the products of the maximal perpendicular diameters of measured lesions (SPD). Measurable extra nodal disease should be assessed in a manner similar to that for nodal disease. For these recommendations, the spleen is considered nodal disease. Disease that is only assessable (e.g., pleural effusions, bone lesions) will be recorded as present or absent only, unless, while an abnormality is still noted by imaging studies or physical examination, it is found to be histologically and pathologically negative.

Response is based on PET/CT based on the revised 2014 Cheson's criteria (Cheson 2014).

PET/CT scans are required at baseline and after 2 cycles of treatment for all patients and should be submitted per instructions in Appendix III.

Response criteria (Cheson, 2014)

	PET-CT Based Response	CT-Based Response
Complete Response	Complete metabolic response (CMR)	Complete radiologic response (CR) (all of the following)
Lymph nodes and extralymphatic sites	Score 1, 2, or 3* with or without a residual mass on 5PS† It is recognized that in Waldeyer's ring or extranodal sites with high physiologic uptake or with activation within spleen or marrow (eg, with chemotherapy or myeloid colony-stimulating factors), uptake may be greater than normal mediastinum and/or liver. In this circumstance, complete metabolic response may be inferred if uptake at sites of initial involvement is no greater than surrounding normal tissue even if the tissue has high physiologic uptake	Target nodes/nodal masses must regress to ≤ 1.5 cm in LDi No extralymphatic sites of disease
Nonmeasured lesion	Not applicable	Absent
Organ enlargement	Not applicable	Regress to normal
New lesions	None	None
Bone marrow	No evidence of FDG-avid disease in marrow	Normal by morphology; if indeterminate, IHC negative

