Partial Response	Partial metabolic response (PMR)	Partial remission (PR) (all of the following)
Lymph nodes and extralymphatic sites	Score 4 or 5† with reduced uptake compared with baseline and residual mass(es) of any size At interim, these findings suggest responding disease At end of treatment, these findings indicate residual disease	≥ 50% decrease in SPD of up to 6 target measurable nodes and extranodal sites When a lesion is too small to measure on CT, assign 5 mm X 5 mm as the default value When no longer visible, 0 X 0 mm For a node > 5 mm X 5 mm, but smaller than normal, use actual measurement for calculation
Nonmeasured lesions	Not applicable	Absent/normal, regressed, but no increase
Organ enlargement	Not applicable	Spleen must have regressed by > 50% in length beyond normal
New lesions	None	None
Bone marrow	Residual uptake higher than uptake in normal marrow but reduced compared with baseline (diffuse uptake compatible with reactive changes from chemotherapy allowed). If there are persistent focal changes in the marrow in the context of a nodal response, consideration should be given to further evaluation with MRI or biopsy or an interval scan	Not Applicable

No Response or Stable Disease	No metabolic response (NMR)	Stable disease (SD)
Target nodes/nodal masses, extranodal lesions	Score 4 or 5 with no significant change in FDG uptake from baseline at interim or end of treatment	< 50% decrease from baseline in SPD of up to 6 dominant, measurable nodes and extranodal sites; no criteria for progressive disease are met
Nonmeasured lesions	Not applicable	No increase consistent with progression
Organ enlargement	Not applicable	No increase consistent with progression
New lesions	None	None
Bone marrow	No change from baseline	Not Applicable
Progressive disease	Progressive metabolic disease (PMD)	Progressive disease (PD) requires at least 1 of the following
Individual target nodes/nodal masses	Score 4 or 5 with an increase in intensity of uptake from baseline and/or	PPD progression:

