consider a score of 3 as inadequate response (to avoid undertreatment). Measured dominant lesions: Up to six of the largest dominant nodes, nodal masses, and extranodal lesions selected to be clearly measurable in two diameters. Nodes should preferably be from disparate regions of the body and should include, where applicable, mediastinal and retroperitoneal areas. Non-nodal lesions include those in solid organs (eg, liver, spleen, kidneys, lungs), GI involvement, cutaneous lesions, or those noted on palpation. Nonmeasured lesions: Any disease not selected as measured, dominant disease and truly assessable disease should be considered not measured. These sites include any nodes, nodal masses, and extranodal sites not selected as dominant or measurable or that do not meet the requirements for measurability but are still considered abnormal, as well as truly assessable disease, which is any site of suspected disease that would be difficult to follow quantitatively with measurement, including pleural effusions, ascites, bone lesions, leptomeningeal disease, abdominal masses, and other lesions that cannot be confirmed and followed by imaging. In Waldeyer's ring or in extranodal sites (eg, GI tract, liver, bone marrow), FDG uptake may be greater than in the mediastinum with complete metabolic response, but should be no higher than surrounding normal physiologic uptake (eg, with marrow activation as a result of chemotherapy or myeloid growth factors).

†PET 5PS: 1, no uptake above background; 2, uptake \leq mediastinum; 3, uptake $>$ mediastinum but \leq liver; 4, uptake moderately $>$ liver; 5, uptake markedly higher than liver and/or new lesions; X, new areas of uptake unlikely to be related to lymphoma.

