- 16.32 **Power and Significance Level:** Assuming that the number of responses is binomially distributed, with a significance level of 9%, the probability of declaring that the regimen warrants further studies (i.e., statistical power) and the probability of stopping after the interim analysis under various response proportions can be tabulated as a function of the true response proportion as shown in the table below.

If the true success proportion is...	0.45	0.50	0.55	0.60	0.65
Then the probability of declaring that the regimen is promising and warrants further study is...	0.090	0.249	0.491	0.735	0.900
And the probability of stopping after the interim analysis is...	0.591	0.412	0.249	0.128	0.053

- 16.33 **Other Considerations:** Toxicity, quality/duration of response, and patterns of treatment failure observed in this study, as well as scientific discoveries or changes in standard care will be taken into account in any decision to terminate the study.
- 16.4 **Analysis Plan:** The analysis for this trial will commence at planned time points (see 16.3) and at the time the patients have become evaluable for the primary endpoint. Such a decision will be made by the Statistician and Study Chair, in accord with CCS Standard Operating Procedures, availability of data for secondary endpoints (eg, laboratory correlates), and the level of data maturity. It is anticipated that the earliest date in which the results will be made available via manuscript, abstract, or presentation format is when the last patient has been followed for at least 2 months.

16.41 **Primary Endpoint:**

16.411 **Definition:** The primary endpoint of this trial is the overall response rate after two cycles of treatment. A response will be defined as a CMR or PMR noted as the objective status after two cycles of treatment. All patients meeting the eligibility criteria who have signed a consent form and have begun treatment will be evaluable for overall response, with the exception of patients who are determined to be a major treatment violation.

16.412 **Estimation:** The proportion of successes will be estimated by the number of successes divided by the total number of evaluable patients.

Confidence intervals for the true success proportion will be calculated according to the approach of Duffy and Santner (Duffy and Santner 1987).

16.42 **Secondary Endpoints:**

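### No minimum baseline uptake is required at entry, so a phase II patient whose disease is all at 5-point score 3 or less is counted as a CMR if nothing changes

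*Combined protocol and SAP*

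**What the plan says.** **Entry.** Section 3.1, item 3.13, requires "Measurable disease (at least 1 lesion ≥ 1.5 cm in diameter) as detected by PET/CT and as defined in Section 11.0". Section 11.1 adds only how lesions are measured: "Lymph node measurements should be taken from the CT portion of the PET/CT, or other dedicated CT scans where applicable". It sets no baseline uptake or 5-point score, and no other inclusion or exclusion criterion does so.

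**Response.** Section 11.1 states: "Response is based on PET/CT based on the revised 2014 Cheson's criteria (Cheson 2014". In the PET-CT column of its table:

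- CMR is "Score 1, 2, or 3* with or without a residual mass on 5PS", with no new lesions and no FDG-avid disease in the marrow.
- PMR is "Score 4 or 5† with reduced uptake compared with baseline and residual mass(es) of any size".
- NMR is "Score 4 or 5 with no significant change in FDG uptake from baseline at interim or end of treatment".
- PMD is score 4 or 5 with increased uptake from baseline, or new FDG-avid foci.

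The scale's footnote places only the top two scores above liver: "4, uptake moderately $>$ liver; 5, uptake markedly higher than liver and/or new lesions".

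**Endpoint and rule.** Sections 16.11 and 16.411 define success: "A response will be defined as a CMR or PMR noted as the objective status after two cycles of treatment". Sections 16.311 and 16.312 stop at 9 or fewer successes in 20 and call the regimen promising at 25 or more in 45. The CMR rate is also a secondary endpoint (16.422).

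**The concern.** Entry is set by lesion size, but success is read from metabolic uptake. The PMR, NMR and PMD rows refer to baseline or to newly appearing disease. The CMR score condition looks only at the level reached after cycle 2. If that level was already present before treatment, the scale has no category for unchanged disease other than CMR.

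The trial has a single arm and is judged against a fixed 45% rate, so no control group carries the same misclassification. Any such patient who stays unchanged adds one success to the 10-of-20 and 25-of-45 counts and to the CMR rate, whether or not the treatment did anything. In the correlative analysis of SUV reduction (16.432) the same patient is a responder with little uptake to reduce, although that analysis plays no part in the decision.

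**Working it through.** **Step 1: classify an unchanged patient.** Take a patient with every site at score 3 or less at baseline, no FDG-avid marrow disease, and the same findings after cycle 2.

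| Category | What the PET-CT column needs | Met? |
|---|---|---|
| CMR | score 1 to 3, no new lesions, no FDG-avid marrow | yes |
| PMR | score 4 or 5, reduced from baseline | no |
| NMR | score 4 or 5, no significant change | no |
| PMD | score 4 or 5 with increase, or new foci | no |

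Only CMR is available. The CT column would call an unchanged lesion larger than 1.5 cm stable disease, but the endpoint is defined by CMR and PMR.

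**Step 2: reproduce the plan's figures.** Inputs are the rules in 16.311 and 16.312. With b the binomial probability,

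P(promising) = sum over x = 10 to 20 of b(x; 20, p) × P(Bin(25, p) ≥ 25 − x), and P(stop at interim) = P(Bin(20, p) ≤ 9).

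| True rate p | P(promising) | 16.32 | P(stop) | 16.32 |
|---|---|---|---|---|
| 0.45 | 0.0903 | 0.090 | 0.5914 | 0.591 |
| 0.50 | 0.2490 | 0.249 | 0.4119 | 0.412 |
| 0.55 | 0.4906 | 0.491 | 0.2493 | 0.249 |
| 0.60 | 0.7352 | 0.735 | 0.1275 | 0.128 |
| 0.65 | 0.9001 | 0.900 | 0.0532 | 0.053 |

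The table in 16.32 is correct for the rates it lists.

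**Step 3: add low-uptake patients.** Let q be the share of evaluable patients with all disease at score 3 or less at baseline, and s their success rate under an ineffective regimen. The other patients respond at 45%. Then

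p = 0.45 × (1 − q) + s × q = 0.45 + (s − 0.45) × q.

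The documents give neither q nor s, so both are assumed. Setting s = 1 is the upper bound; s = 0.70 is an illustration that allows for failures. For example, at q = 2%, p = 0.45 + 0.55 × 0.02 = 0.461 for s = 1 and p = 0.45 + 0.25 × 0.02 = 0.455 for s = 0.70.

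| q | Expected number in 45 | p, s = 1 | P(promising) | p, s = 0.70 | P(promising) |
|---|---|---|---|---|---|
| 0 | 0 | 0.4500 | 0.0903 | 0.4500 | 0.0903 |
| 1% | 0.45 | 0.4555 | 0.1028 | 0.4525 | 0.0958 |
| 2% | 0.90 | 0.4610 | 0.1165 | 0.4550 | 0.1016 |
| 5% | 2.25 | 0.4775 | 0.1650 | 0.4625 | 0.1205 |

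The 0.1165 entry is 0.11651 before rounding, hence 0.117; the 0.1205 entry is 0.12046, hence 0.120.

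**Cross-check.** With exactly one certain success placed at random among the 45, and the other 44 responding at 45%, P(promising) is 0.1168, close to the 2% row for s = 1.

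All these figures assume that no such patients contributed to the 45% benchmark in 16.31. If some did, part of the effect is already in the benchmark and the excess is smaller.

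**The case against.** A reader might infer that these patients are automatic successes, and that the true type I error is therefore well above the 9% stated in 16.32. The documents do not support that.

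- **They can fail.** A rise to score 4 or 5, or new FDG-avid foci, is PMD. Under 16.411 and 16.412 a treated, eligible patient without a major violation stays in the denominator, so one who has no cycle 2 response is not a success. Progression is what one would expect under an ineffective regimen in relapsed or refractory disease. The s = 1 figures are therefore upper bounds.
- **The group is narrow.** Detection by PET/CT can reasonably be read as needing a PET-visible lesion, which may exclude score 1. Every site must be at or below liver, not just one lesion, and the marrow must be free of FDG-avid disease. Phase II is limited to DLBCL.
- **Its frequency is unknown.** Nothing in the documents supports a particular q, and zero is possible.
- **Much of the data exists.** Baseline PET/CT is mandatory and the images are submitted (Sections 4.0 and 11.1). The SUV analysis in 16.432 already needs baseline values, so a sensitivity analysis is possible without changing eligibility.

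These points stand, and they reduce the size and priority of the concern. They do not close the gap. Scores 2 and 3 remain compatible with 3.13. The footnote under which score 3 may be treated as inadequate concerns de-escalation trials, and this protocol does not adopt it. Item 3.15 allows steroids and/or rituximab for symptoms up to one week before registration, and the baseline scan may be up to 21 days before registration, so treatment before the scan is one possible route to low baseline uptake. The sensitivity analysis, though feasible, is not pre-specified.

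**Conclusion.** The concern holds in a limited form. Entry has no baseline uptake floor, and a patient whose disease is all at score 3 or less at baseline is counted as CMR, and so as a success, if metabolically unchanged after cycle 2. No figure in 16.32 is wrong; the gap is a possible route by which the false-positive probability could exceed the stated 9%.

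For q between 0 and 5%, that probability runs from 0.090 to an upper bound of 0.165, or to about 0.12 if 70% of these patients succeed. This rests on an assumed q, an assumed s, a 45% response rate in all other patients, and a benchmark free of such patients. Since q is probably small in DLBCL and may be zero, this is an inexpensive improvement of low priority and not a defect that undermines the design.

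**What to change.** 1. For phase II, amend 3.13 to require at least one lesion of 1.5 cm or more with a baseline 5-point score of 4 or 5.
2. Record the baseline score, for example as a field on the baseline Measurement form listed in Section 18.1.
3. For patients already enrolled, leave the primary count and the decision rule as they are. Pre-specify in 16.41 and 16.42 a sensitivity analysis of the ORR and the CMR rate that excludes patients with a baseline score of 3 or less. Include the phase I DLBCL patients treated at the MTD, who count toward phase II under 16.12 and would not have been screened by the amended criterion.

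The cost is one phrase in the eligibility criteria, one form field and one sentence in the analysis plan. No new procedure is needed, because the baseline PET/CT is already required. The downside is that an occasional patient with low-uptake disease would not be eligible for phase II.

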As noted above, patients tolerated the addition of 25 mg dose daily of lenalidomide from days 1-7 of a 14-day cycle of R-ICE chemotherapy without need for any dose modifications. For eight of the fifteen patients, the cycle was every 21 days (Feldman et al., 2014).

Previously, our group was able to show that lenalidomide could be safely added to the R-CHOP regimen (R2CHOP). There were no dose limiting toxicities with the 25 mg daily dose for days 1 through 10 (Nowakowski et al., 2011).

Other examples of dosing and schedules of regimens where lenalidomide is added to other chemotherapy regimens include:

- Bendamustine/Dexamethasone; every 28days; Lenalidomide 15 mg 1 through 21 days
- Bortezomib/Dexamethasone; every 21 days; Lenalidomide 25 mg Days 1 through 14
- BiRD (Biaxin [clarithromycin] / Revlimid [lenalidomide] / dexamethasone) every 28 days; Lenalidomide 25 mg Days 1 through 21

There is also evidence to suggest that it is not only the dose but the duration of exposure to lenalidomide that is important in its role as an immunomodulatory agent.

Based on this and consensus between our experts we plan on dosing lenalidomide days 1 through 14 in a 21 day treatment cycle of R-ICE as noted in Table 7.1. We will start with 15 mg daily and escalate to 20 mg daily as noted by Feldman and colleagues but with a longer duration for 14 days instead of 7 days. There are adjustment to doses based on renal function outlined by the manufacturer and other studies, however, for the purposes of the study, patients would need a creatinine ≤ 2.0 mg/dL or calculated creatinine clearance must be ≥ 30 ml/min using the Cockcroft-Gault formula to be eligible for the study.

A cycle of R2ICE versus RICE chemoimmunotherapy would be 21 days. For the first stage of the study to determine the MTD, building upon the work published on the 'RICER' regimen of Feldman and colleagues, a 3 x 3 dose-escalation design would be used, in which a cohort of three consecutive patients would be assigned initially to the lowest dose of lenalidomide in combination with RICE (Feldman et al., 2014). If no patient developed a dose-limiting toxicity (DLT) during cycle 1 (one cycle being 21 d), the subsequent cohort of three patients would be assigned to the next dose. If any patient in any cohort developed a DLT, that cohort would be expanded by another three patients. In the absence of a DLT being identified, the 20 mg cohort would be expanded to a total of six patients in the current study.

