In the original study of the RICER, lenalidomide was dosed for 7 days and the following 4 cohorts were used (Feldman, Mato et al. 2014):

- Cohort 1: RICE + Lenalidomide 10mg days 1-7
- Cohort 2: RICE + Lenalidomide 15mg days 1-7
- Cohort 3: RICE + Lenalidomide 20mg days 1-7
- Cohort 4: RICE + Lenalidomide 25mg days 1-7

For the purposes of this study, the same cohorts would be expanded to have lenalidomide given 14 days per 21 days cycle instead of the 7 days as noted above.

For the second phase of the study, patients will be treated with the MTD determined by Lenalidomide plus R-ICE (R2ICE regimen) from stage I (Figure 3).

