 - Phase I subjects must have calculated creatinine clearance $\geq 60\text{ml}/\text{min}$ by Cockcroft-Gault formula.

- Phase II subjects must have calculated creatinine clearance ≥ 30 ml/min by Cockcroft-Gault formula. See section below, “Dosing Regimen”, regarding lenalidomide dose adjustment for calculated creatinine clearance ≥ 30 ml/min and < 60 ml/min.

Cockcroft-Gault Equation:

$$\text{Creatinine clearance for males} = \frac{(140 - \text{age})(\text{weight in kg})}{(72)(\text{serum creatinine in mg/dL})}$$

$$\text{Creatinine clearance for females} = \frac{(140 - \text{age})(\text{weight in kg})(0.85)}{(72)(\text{serum creatinine in mg/dL})}$$

- 3.18 For women of childbearing potential only: Negative pregnancy test ≤ 10 -14 days prior to registration. NOTE: the patient must have an additional negative pregnancy test ≤ 24 hours prior to receiving the initial prescription of lenalidomide, per requirements of the REVLIMID REMS™ program.
- 3.19a Provide informed written consent.
- 3.19b Willing to return to enrolling institution for follow-up (during the Active Monitoring Phase of the study (i.e.active treatment and observation)).
- 3.19c Willing to provide blood samples for correlative research purposes (see Sections 4, 6.22, 14.0).
- 3.19d Considered transplant-eligible, as determined by the opinion of the investigator at the participating institution. The participating institution does not need to be a transplant center but patients can be referred to a transplant center if needed.
- 3.19e Willing and able to register into and comply with the mandatory requirements of Celgene’s REVLIMID REMS™ program.
- 3.19f Females of reproductive potential are willing and able to adhere to the scheduled pregnancy testing as required by Celgene’s REVLIMID REMS™ program.
- 3.19g Willing and able to take aspirin (81mg) daily as prophylactic anticoagulation (patients intolerant to ASA may use warfarin or low molecular weight heparin).
- 3.2 Exclusion Criteria
- 3.21 Any of the following because this study involves an agent that has known genotoxic, mutagenic and teratogenic effects:
- Pregnant women
 - Nursing women
 - Men or women of childbearing potential who are unwilling to employ adequate contraception

NOTE: Patients unwilling or unable to do any of the following are also excluded:

- Men must agree to use a latex condom during sexual contact with a female of child-bearing potential even if they have had a successful vasectomy.

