7.12 Phase II

R2ICE Treatment Schedule: Cycle length is 21 days.

Agent	Dose ¹	Route	Day
Lenalidomide ²	As determined by phase I	PO	As determined by phase I
Aspirin ²	81 mg	PO	Days 1-14
Rituximab ³	375 mg/m ²	IV	Day 1
Ifosfamide	5000 mg/m ²	IV	Day 2
Mesna	5000 mg/m ²	IV	Day 2
Carboplatin	AUC 5	IV	Day 2
Etoposide	100 mg/m ²	IV	Days 1-3
Pegfilgrastim ⁴	6 mg	SubQ ⁴	Day 4
Dexamethasone ⁵	20 mg	IV ⁵	Day 1-2
Tumor lysis prophylaxis ⁶			

- 1 Body surface area based on actual body weight
- 2 For patients on the R2-ICE arm taking Lenalidomide, low dose Aspirin 81 mg daily will continued till the platelet counts fall below 50,000. Patients who cannot take aspirin will be placed on prophylactic warfarin or low molecular weight heparin (Lovenox 40 mg daily) until the platelet counts fall below 50,000. Lenalidomide is provided at no charge to patients by Celgene Corporation for patients on the R2ICE arm.
- 3 Rituximab may be rounded to nearest 50 mg. Patients will get acetaminophen 1000 mg/dose 30 minutes prior to infusion and every 4 hours as needed for infusion related reactions. In addition, diphenhydramine 50 mg/dose 30 minutes prior and then 25 mg/dose IV every 4 hours as needed for infusion related reactions with rituximab. This may be repeated once if symptoms are not relieved within 15 minutes of initial dose. Meperidine 25 mg/dose IV push prn rigors, may repeat once if first dose ineffective.
- 4 Pegfilgrastim should be given 18 hours after chemotherapy on Day 4-5. G-CSF (filgrastim) or other growth factors can be used (instead of Pegfilgrastim) based on institutional practice.
- 5 Dexamethasone 20 mg IV Day 1 and 2; 30 minutes prior to Rituximab and Carboplatin to prevent reactions.
- 6 Tumor lysis prophylaxis per institutional practice. For patients with AKI, large tumor burden and/or uric acid > 8 mg/dl, consideration should be given to giving rasburicase 6 mg IV once and repeated as needed.

7.2 Length of Treatment: Patients will receive treatment per protocol for 2 cycles. At the end of 2 cycles, patients who are CMR, PMR, or NMR may receive a 3rd and 4th cycle of treatment per physician discretion.

7.3 Stem Cell Transplant (SCT): After the completion of 2 cycles of R2ICE treatment, patients who have achieved an objective status of CMR, PMR or NMR may proceed to SCT during the event monitoring phase. The SCT should be recorded on the event

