8.0 Dosage Modification Based on Adverse Events

Dose adjustments of ICE chemotherapy are to be performed per institutional standards. All patients will receive prophylactic hematopoietic growth factors (e.g., granulocyte-colony stimulating factor [G-CSF]) to shorten the period of neutropenia and transfusions of blood products should be provided during the course of treatment per institutional guidelines.

Standard practice and local prescribing information will be followed for rituximab and background chemotherapy. Omitting or discontinuing background therapy must lead to omitting or discontinuing of lenalidomide as well.

Dose Modifications at the start of next treatment cycles:

Dose modifications of Lenalidomide will be based on the dose levels as noted in Table 8.1 and on adverse events noted during preceding cycles (see Table 8.2 for guidance regarding dose reductions based on adverse events).

Dose modifications during a treatment cycle:

Please note, while patient is actively on Lenalidomide, modifications are not allowed during the particular treatment cycle and are only allowed Day 1 of any particular cycle. Decreasing by one dose level would be for the next cycle of treatment. During active treatment cycle, treatment can be held for up to 7 days if needed.

If multiple adverse events are seen, administer dose based on greatest reduction required for any single adverse event observed. Reductions apply to treatment given in the preceding cycle and are based on adverse events observed since the prior dose.

ALERT: ADR reporting may be required for some adverse events (See Section 10)

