8.1 Dose Levels (Based on Adverse Events in Table 8.2)

Lenalidomide*				
	Starting Dose 20 mg days 1-14	Starting Dose 15 mg days 1-14	Starting Dose 10 mg days 1-14	Starting Dose 10 mg days 1-10
1 st dose reduction	15 mg days 1-14	10 mg days 1-14	10 mg days 1-10	10 mg Daily for days 1-7
2 nd dose reduction	10 mg days 1-14	10 mg days 1-10	10 mg Daily for days 1-7	Discontinue
3 rd dose reduction	10 mg days 1-10	10 mg Daily for days 1-7	Discontinue	
4 th dose reduction	10 mg Daily for days 1-7	Discontinue		
5 th dose reduction	Discontinue			

* Cycle length is 21 days for all treatment cycles

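### Phase II admits patients with creatinine clearance 30 to <60 ml/min and promises them a lenalidomide adjustment, but the visible protocol body states no adjusted dose

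*Combined protocol and SAP*

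**What the plan says.** - **Eligibility (3.17).** "Phase I subjects must have calculated creatinine clearance" of at least 60 ml/min; phase II patients need only 30. For phase II patients from 30 to <60 the criterion refers to a section further on, named Dosing Regimen, "regarding lenalidomide dose adjustment for calculated creatinine clearance".
- **Phase II schedule (7.12).** The lenalidomide dose and days are both given as "As determined by phase I". None of the six footnotes mentions renal function.
- **Background (1.2).** In the second phase "patients will be treated with the MTD determined by Lenalidomide plus R-ICE", with no renal exception. Section 16.12 likewise accrues phase II patients at the MTD level. Section 1.2 also remarks that "There are adjustment to doses based on renal function outlined by the manufacturer and other studies", but then gives only an entry limit for this study.
- **Dose changes (8.0 to 8.2).** The lenalidomide ladder is headed "Dose Levels (Based on Adverse Events in Table 8.2"). For timing, "modifications are not allowed during the particular treatment cycle and are only allowed Day 1 of any particular cycle". Section 8.0 separately allows treatment to be paused for up to 7 days.
- **Elimination (15.15).** Mainly renal: 65% to 85% leaves unchanged in urine when renal function is normal.

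**The concern.** The authors had already decided that patients with clearance 30 to <60 need a different lenalidomide dose, since 3.17 says an adjustment exists. A site that opens the phase II schedule to write the first prescription finds only the phase I dose. That dose was established, on 3.17's own limits, with no patient who entered below 60 ml/min.

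If the site follows the schedule, cycle 1 is given at full dose on top of R-ICE, and reduction comes only in a later cycle, after an adverse event. If sites instead work out their own adjustments, the phase II regimen differs between them. Section 10.336 also defines an oral overdose as any amount above the dose the protocol specifies, which cannot be applied consistently when the intended dose is not written down.

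**Working it through.** The plan states no figure for this point. The check is a comparison of text, followed by an illustration of size.

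**Step 1. Where could a cycle 1 dose for clearance 30 to <60 be set?**

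| Place | What it governs | Dose for 30 to <60? |
|---|---|---|
| 3.17 | Entry; says an adjustment applies | None; refers onward |
| 7.1, 7.12 | Phase II schedule | Phase I dose, no renal row or footnote |
| 1.2, 16.12 | Background, sample size | MTD, no exception |
| 8.0 | "Standard practice and local prescribing information will be followed for rituximab and background chemotherapy" | That sentence does not cover lenalidomide |
| 8.1, 8.2 | Lenalidomide after adverse events, from a later cycle | Cannot set cycle 1 |
| 15.1 | General pointer to Investigator's Brochure and package insert | States no dose |
| 3.0 | Call the Registration Office for dose level | States no dose; 12.1 records an office-assigned level for phase I only, and 6.2 registers phase II by web |

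No visible place supplies the dose. Creatinine is measured on Day 1 of each cycle (test schedule), but no lenalidomide rule uses it.

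**Step 2. How much could it matter?**

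Input from the documents: fraction excreted unchanged, fe = 0.65 to 0.85 (15.15). Assumptions not in the documents: fe is the renal share of total clearance; renal drug clearance is proportional to creatinine clearance; non-renal clearance is unchanged; normal creatinine clearance (ref) is 90 to 120 ml/min.

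Relative drug clearance at creatinine clearance c: CL(c) = 1 − fe × (1 − c/ref). Exposure on the same dose, relative to 60 ml/min (the lowest clearance phase I admits): CL(60)/CL(c).

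| fe | ref | CL(60) | CL(45) | CL(30) | Ratio at 45 | Ratio at 30 |
|---|---|---|---|---|---|---|
| 0.65 | 90 | 0.783 | 0.675 | 0.567 | 1.16 | 1.38 |
| 0.65 | 120 | 0.675 | 0.594 | 0.513 | 1.14 | 1.32 |
| 0.85 | 90 | 0.717 | 0.575 | 0.433 | 1.25 | 1.65 |
| 0.85 | 120 | 0.575 | 0.469 | 0.363 | 1.23 | 1.59 |

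Ranges: 1.32 to 1.65 at 30 ml/min, 1.14 to 1.25 at 45, and about 1.01 at 59. At 30 ml/min, 20 mg would act like 20 × 1.317 = 26.3 to 20 × 1.654 = 33.1 mg at 60 ml/min; 15 mg like 19.8 to 24.8 mg.

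**Step 3. What reduction would offset this, and does the existing ladder provide it?**

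Reduction needed at 30 ml/min = 1 − 1/ratio: 1 − 1/1.317 = 24% to 1 − 1/1.654 = 40%.

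Daily-dose steps in Table 8.1: 20 to 15 mg is 25%; 15 to 10 mg is 33%; 20 to 10 mg (two steps) is 50%. Below 10 mg for 14 days the ladder shortens the course to 10 and then 7 days, and the daily dose stays at 10 mg. One step from 20 or 15 mg reaches the low end of the range but not 40%. From 10 mg the ladder offers no daily reduction at all.

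**The case against.** **A reader might infer that the protocol orders the full dose for these patients and so contradicts itself.** It does not go that far. The 7.12 entry is a placeholder written before the MTD was known, Sections 1.2 and 16.12 are general statements, and 3.17 is the specific provision. Taken together this is a cross-reference that leads nowhere. A site that checks 3.17 carefully may well query the dose before giving it. An absolute dose could not have been written in advance, though a rule relative to the MTD could.

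**A reader might infer that no rule exists anywhere.** Pages were removed from the copy reviewed, so that cannot be shown. But 3.17 points to a section below it, and nothing in the visible Sections 7 and 8, including the heading 7.1, carries a renal rule.

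**A reader might infer that Section 8 allows interruption only for non-hematologic events of grade 3 or more.** Table 8.2 is worded that way, but Section 8.0 permits a pause of up to 7 days with no grade threshold. Blood counts twice weekly, growth factor for all patients and the phase II adverse event stopping rule add protection. These respond to toxicity; none sets the starting dose.

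**A reader might infer that 26 to 33 mg equivalents exceed what is tolerable.** The documents do not show this. Escalation in 7.61 ends at 20 mg by design, and Section 1.2 reports 25 mg tolerated with R-ICE for 7 days and with R-CHOP for 10, both shorter courses than the 14 days planned here.

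The Investigator's Brochure, the package insert and the Registration Office remain real but partial controls: they give a prescriber somewhere to ask and state no dose for this regimen.

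**Conclusion.** The gap stands. Patients with clearance 30 to <60 ml/min may enter phase II, an adjustment is promised, and the visible body never gives one. Dosing by 7.12 as written means a full starting dose established only at clearance of at least 60. This conclusion rests on the text alone, taking 3.17 as governing eligibility over the looser renal wording in Section 1.2.

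The size is only illustrative. It depends on the assumptions in the working, is largest near 30 ml/min and almost vanishes near 60. How many phase II patients would fall in the range is not given, so no effect on overall toxicity or on the response rate can be calculated, and none is claimed.

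Because the gap concerns the first dose of a mainly renally cleared study drug, it should be closed before phase II opens.

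**What to change.** 1. Add to 7.12 a reduced starting rule for lenalidomide at clearance 30 to <60 ml/min, stated relative to the MTD so that it can be written now. The sponsor should choose the value; none is proposed here. The rule should lower the daily dose and not only the number of days.
2. If the chosen level is not already a starting dose in Table 8.1, add a matching column so that later reductions are defined. This will be needed if the MTD is a 10 mg level, since the table has no lower daily dose. Section 15.12 lists capsules of 5 mg and below.
3. Point the 3.17 cross-reference to the new text in 7.12.

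The cost is a short wording amendment and possibly one table column, with no added patients or procedures. The downside is possibly lower lenalidomide exposure, and so possibly lower activity, in patients near 60 ml/min, whose clearance calls for little reduction. The sponsor can weigh that when choosing the rule.
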